3.2 Study schema

Screening phase

Screening will occur between Day -28 and Day -1. The purpose of the screening period is to establish protocol eligibility. Informed consent will be obtained up to 4 weeks prior to Cycle 1 Day 1 and after the study has been fully explained to each subject and prior to the conduct of any screening procedures or assessments.

The purpose of the baseline visit is to establish disease characteristics prior to allocation and treatment and to confirm protocol eligibility as specified in the inclusion/exclusion criteria. Results of baseline assessments must be obtained prior to the first dose of study drug (Cycle 1/Day 1). Baseline assessments may be performed on Day -1 or on Cycle 1/Day 1 prior to dosing. Clinical laboratory tests including pregnancy test (where applicable) can be performed within 72 hours of the first dose of study drug. Subjects who complete the baseline visit and continue to meet the criteria for inclusion/exclusion will begin the treatment phase of this study.

Determinations performed by routine clinical practice before signing the informed consent will be valid, provided they are carried out following this protocol requirements and date of baseline TC is performed within the previous 4 weeks from treatment initiation. It should be clearly stated that patient consented her/his participation to ESR 15-11561-61-DUNE trial in patient record.

Treatment phase

The treatment phase will begin at the time of allocation of the first patient and will consist of the study treatment cycles. The treatment phase will end when the last patient discontinue the study drug.

The treatment phase will include two stages for each cohort. The first stage will dose the first patient in each cohort in a safety run period for one cycle (4 weeks). If no unexpected side effects are observed in the first patient treated in each cohort during the safety run period, recruitment will continue up to 31 patients for cohorts 1 to 3, and 33 for cohort 4.

Subjects will be allocated in each primary tumor cohort to receive durvalumab 1500 mg Q4W for 12 months plus tremelimumab 75 mg Q4W for up to 4 doses during the first 4 cycles of combined therapy. Cycles are defined by 4 weeks or 28 days. Subjects will undergo safety and efficacy assessment as defined per protocol.

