6.2 Dose Modification and Toxicity Management

6.2.1 Durvalumab and tremelimumab

For adverse events (AEs) that are considered at least partly due to administration of durvalumab and/or tremelimumab the following dose adjustment guidance may be applied:

- Treat each of the toxicities with maximum supportive care (including holding the agent suspected of causing the toxicity where required).
- If the symptoms promptly resolve with supportive care, consideration should be given to continuing the same dose of durvalumab or tremelimumab along with appropriate continuing supportive care. If medically appropriate, dose modifications are permitted for durvalumab and tremelimumab (see Appendix 1).
- All dose modifications should be documented with clear reasoning and documentation of the approach taken.

In addition, there are certain circumstances in which durvalumab or tremelimumab should be permanently discontinued.

Following the first dose of durvalumab or tremelimumab, subsequent administration of durvalumab or tremelimumab can be modified based on toxicities observed (see Appendix 1).

Clinical Study Protocol
 Drug Substance DURVALUMAB/TREMELIMUMAB
 Study Number ESR 15-11561-61-DUNE
 EudraCT Nº: 2016-002858-20
 Edition Number: 5.0 dated on June 09th, 2021

Based on the mechanism of action of durvalumab or tremelimumab leading to T-cell activation and proliferation, there is the possibility of observing immune related Adverse Events (irAEs) during the conduct of this study. Potential irAEs include immune-mediated enterocolitis, dermatitis, hepatitis/hepatotoxicity, endocrinopathy, pneumonitis, nephritis, pancreatitis and neuropathy or neurologic events. Subjects should be monitored for signs and symptoms of irAEs. In the absence of an alternate etiology (e.g., infection or PD) signs or symptoms of enterocolitis, dermatitis, hepatitis/hepatotoxicity, endocrinopathy, pneumonitis, nephritis, pancreatitis and neuropathy or neurologic events should be considered to be immune-related.

Dose modification recommendations and toxicity management guidelines for immune-mediated reactions, for infusion-related reactions, and for non-immune-mediated reactions are detailed in Appendix 1.

In addition, management guidelines for adverse events of special interest (AESIs) are detailed in Section 10.1.3. All toxicities will be graded according to NCI CTCAE v4.03.

7. RESTRICTIONS DURING THE STUDY AND CONCOMITANT TREATMENT(s)

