- Administer study drugs. (from C5D1 to C12D1 tremelimumab no longer administered, only durvalumab).
- Record all concomitant medication use.
- Record any AEs or SAEs.
- Record survival data.
- Tumor assessment every 12 weeks until confirmed PD.

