8.1.3 End of Treatment

End of treatment is defined as the last planned dosing visit within the 12-month dosing period. For subjects who discontinue durvalumab or tremelimumab prior to 12 months, end of treatment is considered the last visit where the decision is made to discontinue treatment. All required procedures may be completed within \pm 7 days of the end of treatment visit. Repeat disease assessment is not required if performed within 28 days prior to the end of treatment visit.

Blood samples for biomarker analysis are collected.

Assessments for subjects who have completed durvalumab and tremelimumab treatment and achieved disease control, or have discontinued durvalumab or tremelimumab due to toxicity in the absence of confirmed progressive disease are provided in APPENDIX 2.

Assessments for subjects who have discontinued durvalumab or tremelimumab treatment due to

Clinical Study Protocol
 Drug Substance DURVALUMAB/TREMELIMUMAB
 Study Number ESR 15-11561-61-DUNE
 EudraCT Nº: 2016-002858-20
 Edition Number: 5.0 dated on June 09th, 2021

confirmed PD are presented in APPENDIX 3.

All subjects will be followed for survival until the end of the study regardless of further treatments, or until the sponsor ends the study.

Follow-up period

TC/MRI every 12 weeks until progression. Monthly visits during the first 3 months after end of treatment, every 2 months until one year, and therefore every 6 months. Determinations to be done are listed in appendix 2 and 3.

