
Zhang et al 2012

Zou and Chen, 2008

Zou W, chen L. Inhibitory B7-family molecules in the tumour microenvironment. Nat Rev Immunol. 2008;8(6):467-77.

Clinical Study Protocol
 Drug Substance DURVALUMAB/TREMELIMUMAB
 Study Number ESR 15-11561-61-DUNE
 EudraCT Nº: 2016-002858-20
 Edition Number: 5.0 dated on June 09th, 2021

Appendix 1. Dosing Modification and Toxicity Management Guidelines (TMGs) for Durvalumab Monotherapy, Durvalumab in Combination with other Products, or Tremelimumab Monotherapy. 17 November 2020.

Note: Annex is to be used in any clinical trial protocol within which patients are treated with Durvalumab Monotherapy, Durvalumab in Combination with other Products, or Tremelimumab

			-

			-
<hr/>			
			-

			-
	•		-
<hr/>			
			-
			-
	•		-

Clinical Study Protocol

Drug Substance DURVALUMAB/TREMELIMUMAB

Study Number ESR 15-11561-61-DUNE

EudraCT Nº: 2016-002858-20

Edition Number: 5.0 dated on June 09th, 2021

			-
			-
			-
	1.		-
	1.		
			-

Clinical Study Protocol

Drug Substance DURVALUMAB/TREMELIMUMAB

Study Number ESR 15-11561-61-DUNE

EudraCT Nº: 2016-002858-20

Edition Number: 5.0 dated on June 09th, 2021

			-
			-
			-
			-
			-
			-

Clinical Study Protocol
Drug Substance DURVALUMAB/TREMELIMUMAB
Study Number ESR 15-11561-61-DUNE
EudraCT Nº: 2016-002858-20
Edition Number: 5.0 dated on June 09th, 2021

General Considerations Regarding Immune-Mediated Reactions

General Considerations Regarding Immune-Mediated Reactions

These guidelines are provided as a recommendation to support investigators in the management of potential immune-mediated adverse events (imAEs).

Immune-mediated events can occur in nearly any organ or tissue, therefore, these guidelines may not include all the possible immune-mediated reactions. Investigators are advised to take into consideration the appropriate practice guidelines and other society guidelines (e.g., NCCN, ESMO) in the management of these events. Refer to the section of the table titled “Other -Immune-Mediated Reactions” for general guidance on imAEs not noted in the “Specific Immune-Mediated Reactions” section.

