Early identification and management of immune-mediated adverse events (imAEs) are essential to ensure safe use of the study drug. Monitor patients closely for symptoms and signs that may be clinical manifestations of underlying immune-mediated adverse events. Patients with suspected imAEs should be thoroughly evaluated to rule out any alternative etiologies (e.g., disease progression, concomitant medications, infections). In the absence of a clear alternative etiology, all such events should be managed as if they were immune-mediated. Institute medical management promptly, including specialty consultation as appropriate. In general, withhold study drug/study regimen for severe (Grade 3) imAEs. Permanently discontinue study drug/study regimen for life-threatening (Grade 4) imAEs, recurrent severe (Grade 3) imAEs that require systemic immunosuppressive treatment, or an inability to reduce corticosteroid dose to 10 mg or less of prednisone or equivalent per day within 12 weeks of initiating corticosteroids.

Based on the severity of the imAE, durvalumab should be withheld and corticosteroids administered. Upon improvement to Grade ≤ 1 , corticosteroid should be tapered over ≥ 28 days. More potent immunosuppressive agents such as TNF inhibitors (e.g., infliximab) should be considered for events not responding to systemic steroids. Alternative immunosuppressive agents not listed in this guideline may be considered at the discretion of the investigator based on clinical practice and relevant guidelines. With long-term steroid and other immunosuppressive use, consider need for *Pneumocystis jirovecii* pneumonia (PJP, formerly known as *Pneumocystis carinii* pneumonia) prophylaxis, gastrointestinal protection, and glucose monitoring.

Dose modifications of study drug/study regimen should be based on severity of treatment-emergent toxicities graded per NCI CTCAE version in the applicable study protocol.

AE Adverse event; **CTC** Common Toxicity Criteria; **CTCAE** Common Terminology Criteria for Adverse Events; **imAE** immune-mediated adverse event; **NCI** National Cancer Institute; **NCCN** National Comprehensive Cancer Network; **ESMO** European Society for Medical Oncology

Pediatric Considerations Regarding Immune-Mediated Reactions

Dose Modifications	Toxicity Management

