	
For patient treated with PDL-1 inhibitors, hold study drug/study regimen until resolution to Grade ≤1; study drug/study regimen can be resumed after completion of steroid taper. Permanently discontinue study drug/study regimen for Grade 3 if toxicity does not improve to Grade ≤1 within 14 days.
 
Permanently discontinue study drug for 1) Grade 3 colitis in patients treated with CTLA-4 inhibitors or 2) Any grade of intestinal perforation in any patient treated with ICI.
	
For Grade 3 or 4
 
 Promptly initiate empiric IV methylprednisolone 1 to 2 mg/kg/day or equivalent. Monitor stool frequency and volume and maintain hydration. 
 Urgent GI consult and imaging and/or colonoscopy as appropriate. If still no improvement within 2 days, continue steroids and promptly add further immunosuppressants (e.g., infliximab at 5 mg/kg IV, may be repeated at 2 and 6 weeks after initial dose at the discretion of the treating provider). Caution: Ensure GI consult to rule out bowel perforation and refer to infliximab label for general guidance before using infliximab. If perforation is suspected, consult a surgeon experienced in abdominal surgery immediately without any delay.
	
Grade 4
 
Permanently discontinue study drug/study regimen.
	

Hepatitis (elevated LFTs)	Any Grade (Refer to NCI CTCAE applicable version in study protocol for defining the CTC grade/severity)	General Guidance	For Any Grade

PLEASE SEE shaded area immediately below this section to find guidance for management of “Hepatitis (elevated LFTs)” in HCC patients
 
Infliximab should not be used for management of immune-related hepatitis.
			
 Monitor and evaluate liver function test: AST, ALT, ALP, and TB. Evaluate for alternative etiologies (e.g., viral hepatitis, disease progression, concomitant medications).
	
Grade 1
 
 No dose modifications. If it worsens, then treat as Grade 2. 		
For Grade 1
 
 Continue LFT monitoring per protocol.

Grade 2

- Hold study drug/study regimen dose until Grade 2 resolution to Grade ≤ 1 .
- If toxicity worsens, then treat as Grade 3 or Grade 4.
- If toxicity improves to Grade ≤ 1 or baseline, resume study drug/study regimen after completion of steroid taper.

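### The Grade 3 diarrhea/colitis cell in Appendix 1 gives two different instructions that both describe a patient with Grade 3 colitis on durvalumab plus tremelimumab, and does not say which governs or which agent is meant

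*Protocol*

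**What the plan says.** Appendix 1 is a generic guideline. Its opening note begins "Note: Annex is to be used in any clinical trial protocol within which patients are treated with Durvalumab Monotherapy" and goes on to combinations and to tremelimumab alone. Its general considerations say "In general, withhold study drug/study regimen for severe (Grade 3) imAEs", and then list circumstances for permanent stopping.

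The Grade 3 cell for diarrhea/colitis has two parts:

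- "For patient treated with PDL-1 inhibitors, hold study drug/study regimen until resolution to Grade ≤1". Treatment can then resume after the steroid taper. It stops permanently if the event has not improved to that level within 14 days.
- "Permanently discontinue study drug for 1) Grade 3 colitis in patients treated with CTLA-4 inhibitors". The same sentence adds a second trigger, intestinal perforation of any grade in any patient on a checkpoint inhibitor.

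On the regimen, section 3.2 says "Subjects will be allocated in each primary tumor cohort to receive durvalumab 1500 mg Q4W for 12 months plus tremelimumab 75 mg Q4W". Section 8.1.2 describes the later cycles: "from C5D1 to C12D1 tremelimumab no longer administered, only durvalumab".

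Two other places bear on stopping a single agent. Section 6.2.1 words its guidance per agent, "including holding the agent suspected of causing the toxicity where required", and refers to Appendix 1 for detail. Section 8.1.3 says "For subjects who discontinue durvalumab or tremelimumab prior to 12 months, end of treatment is considered the last visit where the decision is made"; the decision meant is the one to stop. The title of Appendix 2 uses the same either-agent wording for follow-up after toxicity.

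**The concern.** The cell is written as if a patient belongs to one drug class or the other. In this trial every patient is assigned both. A site that reads the first sentence may hold and later resume. A site that reads the second may stop for good. Each can say that it followed the Protocol.

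This is first a safety matter, because the cell is a stopping rule. Colitis and diarrhoea are also the two most frequent reactions in the section 1.4.2.3 table of expected serious reactions for the combination. There is a smaller consequence for the analysis. Section 11.2 treats discontinuation of treatment as a censoring reason for survival endpoints, so the same event could be handled differently in the data according to the site's reading. Section 10.3 records the action taken for the two drugs as a pair, so the reading a site used may not show in the adverse event record.

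**Working it through.** **Which sentence applies to whom**

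- Grade 3 colitis on the combination: both sentences fit, and the cell gives no order between them.
- Grade 3 colitis on durvalumab alone: the hold sentence fits. The permanent-stop sentence fits only if earlier tremelimumab counts as treatment with a CTLA-4 inhibitor, and the cell does not say.
- Grade 3 diarrhea without colitis or perforation: only the hold sentence fits, so there is no conflict.
- Perforation, or a Grade 4 event: permanent stop whatever the drug class, so there is no conflict.

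**Which agent stops.** The hold sentence and the Grade 4 line refer to the study drug or the study regimen. The CTLA-4 sentence refers to the study drug only. It could mean tremelimumab or both agents.

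**Is there a tie-breaker elsewhere?** Section 6.2.1 sends the reader back to Appendix 1. Section 4.3 item 5 points to section 10.3 for adverse events that require discontinuation, but section 10.3 covers recording and gives no colitis criterion. Section 4.3 item 2 leaves stopping to the judgement of the investigator or sponsor. None of these settles the cell.

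**Scale.** The plan states no figure on this point, so there is none to reproduce. The inputs are the pooled combination table in section 1.4.2.3 (N = 2068) and the planned sample of 126, with 31 in each of cohorts 1 to 3.

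- Colitis 40, enterocolitis 6, autoimmune colitis 5: 40 + 6 + 5 = 51.
- Rate: 51/2068 = 2.47%, if no patient has two of these terms.
- Expected in 126 patients: 126 × 0.0247 = 3.1.
- Chance of at least one in 126: 1 − (1 − 0.0247)^126 = 0.96.
- Expected in a cohort of 31: 31 × 0.0247 = 0.76.
- Chance of at least one in 31: 1 − (1 − 0.0247)^31 = 0.54.

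The table counts suspected serious reactions and leaves out life-threatening and fatal ones. Section 10.2.1 says that a Grade 3 event need not be serious. The documents give no Grade 3 colitis rate, so these figures show order of magnitude only.

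**Dates.** Section 13.6 projects the last subject in for December 2019. Four doses at four-week intervals fall at weeks 0, 4, 8 and 12, so the last first-course combination dose falls at about the end of March 2020. Adding the 12-week limit for a toxicity delay in section 4.3 item 10 moves this to about June 2020. This version of Appendix 1 is dated 17 November 2020, and the Protocol edition June 2021. On those dates the current text reaches late durvalumab-alone cycles. It also reaches the single retreatment course in section 5.2.2, which again gives four combination doses and then nine of durvalumab alone.

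**The case against.** The best defence is that the cell is a rule followed by overrides. The perforation trigger covers every patient on a PD-L1 inhibitor, so it makes sense only as an override of hold-and-resume. The CTLA-4 trigger sits in the same list and can be read the same way. The general considerations have a similar shape, a general rule and then exceptions. This reading is plausible, but the cell does not state it. Even if it is accepted, it does not say whether one agent or both stop, or whether earlier tremelimumab counts in the durvalumab-alone phase.

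The guidelines are also offered as recommendations, the study physician can be contacted, and SAP section 1.3 already tabulates cycles received, delayed and omitted for each drug. These reduce the practical risk without giving sites a single answer.

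A reader might infer more than the documents support, in four ways:

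- That the whole diarrhea/colitis row conflicts. The CTLA-4 trigger names colitis only.
- That sections 6.2.1 and 8.1.3 contradict each other. Section 6.2.1 gives dosing guidance per agent and does not say that the other agent may continue after a permanent stop. Section 8.1.3 defines a visit. Appendix 3, though titled for patients who have discontinued, also covers some who continue durvalumab, so such titles are not dosing bans. The wording is loose, but a contradiction is not shown.
- That about 6 patients are affected, by adding the 47 diarrhoea reports (98/2068 = 4.7%), or about 19, by applying to 126 the roughly 15% in section 1.4.2.3 who stopped for an adverse event. Diarrhoea lies outside the disputed trigger. The 15% covers any event at any time, including after tremelimumab has finished.
- That sites will deliver different regimens. The text supports only that they may.

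**Conclusion.** The point holds for Grade 3 colitis. While a patient is on the combination, both instructions apply and no order is given. On durvalumab alone, the status of earlier tremelimumab is undefined. In either phase the agent to be stopped is unclear. Few patients are likely to be involved: about 3 of 126, and under one expected per cohort of 31. That assumes the pooled serious-reaction rate is a fair stand-in for the unknown Grade 3 rate, that no patient has two of the terms, and that the text applies throughout treatment. On the projected dates it applies mainly to durvalumab-alone cycles and to retreatment, so the number exposed to this wording is probably smaller. The documents do not show what guideline text applied earlier. Any effect on the nine-month endpoints is likely to be small, and it has not been quantified. The reason to act is that a safety stopping rule should have one reading. Which clinical rule is right is not a question for this review.

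**What to change.** The sponsor must reconcile the two sentences for this trial, with one instruction for the combination phase, including retreatment, and one for the durvalumab-alone phase. Each should name the agent or agents it applies to, and the second should say whether earlier tremelimumab counts. The sponsor's medical team decides the clinical content.

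As a secondary clarification, sections 6.2.1 and 8.1.3 and Appendix 2 should use the same wording on whether stopping one agent ends study treatment. Read literally, section 8.1.3 could also catch a patient who stops tremelimumab as planned after cycle 4.

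The cost is a site clarification letter or amendment text, with brief re-training. No change to the sample size or to the primary analysis is needed.

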AEs of infusion reactions (also termed infusion-related reactions) are of special interest to [REDACTED] and are defined, for the purpose of this protocol, as all AEs occurring from the start of IP infusion up to 48 hours after the infusion start time. For all infusion reactions, SAEs should be reported to the sponsor as described in Section 10.3.

Hypersensitivity reactions

Hypersensitivity reactions as well as infusion-related reactions have been reported with anti-PD-L1 and anti-PD-1 therapy (Brahmer et al 2012). As with the administration of any foreign protein and/or other biologic agents, reactions following the infusion of mAbs can be caused by various mechanisms, including acute anaphylactic (IgE-mediated) and anaphylactoid reactions against the mAbs and serum sickness. Acute allergic reactions may occur, may be severe, and may result in death. Acute allergic reactions may include hypotension, dyspnea, cyanosis, respiratory failure, urticaria, pruritus, angioedema, hypotonia, arthralgia, bronchospasm, wheeze, cough, dizziness, fatigue, headache, hypertension, myalgia, vomiting, and unresponsiveness. Guidelines for the management of patients with hypersensitivity (including anaphylactic reaction) and infusion-related reactions are provided in Appendix 1.

Hepatic function abnormalities (hepatotoxicity)

Hepatic function abnormality is defined as any increase in ALT or AST to greater than $3 \times$ ULN and concurrent increase in total bilirubin to be greater than $2 \times$ ULN. Concurrent findings are those that

Clinical Study Protocol
 Drug Substance DURVALUMAB/TREMELIMUMAB
 Study Number ESR 15-11561-61-DUNE
 EudraCT Nº: 2016-002858-20
 Edition Number: 5.0 dated on June 09th, 2021

derive from a single blood draw or from separate blood draws taken within 8 days of each other. Follow-up investigations and inquiries will be initiated promptly by the investigational site to determine whether the findings are reproducible and/or whether there is objective evidence that clearly supports causation by a disease (eg, cholelithiasis and bile duct obstruction with distended gallbladder) or an agent other than the IP. Guidelines for management of patients with hepatic function abnormality are provided in section 10.3.3.2.

For the consultation of the complete list of adverse events see the last version of IB provided in the ISF.

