10.3.3.2 Hepatic function abnormality

Hepatic function abnormality (as defined in Section 10.1.3.) in a study subject, with or without associated clinical manifestations, is required to be reported as "hepatic function abnormal" **within 24 hours of knowledge of the event** to the sponsor, who will send a copy to [REDACTED] Patient Safety, using the designated Safety e-mailbox (see Section 10.3.2 for contact information), unless a definitive underlying diagnosis for the abnormality (e.g.,

Clinical Study Protocol
 Drug Substance DURVALUMAB/TREMELIMUMAB
 Study Number ESR 15-11561-61-DUNE
 EudraCT Nº: 2016-002858-20
 Edition Number: 5.0 dated on June 09th, 2021

cholelithiasis or bile duct obstruction) that is unrelated to investigational product has been confirmed.

- If the definitive underlying diagnosis for the abnormality has been established and is unrelated to investigational product, the decision to continue dosing of the study subject will be based on the clinical judgment of the investigator.
- If no definitive underlying diagnosis for the abnormality is established, dosing of the study subject must be interrupted immediately. Follow-up investigations and inquiries must be initiated by the investigational site without delay.

Grade 1-2 events should be considered AEs, not SAEs. However, Grade 1-2 events should be reported as SAEs if requires hospitalization or if they are medically important events based on the investigator judgement.

Grade 3 events, should be reported as SAE if requires hospitalization or if they are medically important events based on the investigator judgement.

All grade 4 events should be reported as SAEs.

Cases where a patient shows elevations in liver biochemistry may require further evaluation and occurrences of AST or ALT $\geq 3 \times$ ULN together with total bilirubin $\geq 2 \times$ ULN may need to be reported as SAEs.

Each reported event of hepatic function abnormality will be followed by the investigator and evaluated by the sponsor.

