- Permanently discontinue study drug/study regimen for any case meeting Hy's law criteria (AST and/or ALT $>3 \times$ ULN + bilirubin $>2 \times$ ULN without initial findings of cholestasis (i.e., elevated alkaline P04) and in the absence of any alternative cause.b

For Grade 2

- Regular and frequent checking of LFTs (e.g., every 1 to 2 days) until LFT elevations improve or resolve.
- If no resolution to Grade ≤ 1 in 1 to 2 days, consider discussing with study physician, as needed.
- If event is persistent (>2 to 3 days) or worsens, promptly start prednisone 1 to 2 mg/kg/day PO or IV equivalent.

Grade 3 or 4

For Grade 3

- For elevations in transaminases $\leq 8 \times$ ULN, or elevations in bilirubin $\leq 5 \times$ ULN:
 - Hold study drug/study regimen dose until resolution to Grade ≤ 1 or baseline
 - Resume study drug/study regimen if elevations downgrade to Grade ≤ 1 or baseline within 14 days and after completion of steroid taper.
 - Permanently discontinue study drug/study regimen if the elevations do not downgrade to Grade ≤ 1 or baseline within 14 days
 - For elevations in transaminases $> 8 \times$ ULN or elevations in bilirubin $> 5 \times$ ULN, discontinue study drug/study regimen.

For Grade 4

- Permanently discontinue study drug/study regimen.

For Grade 3 or 4

- Promptly initiate empiric IV methylprednisolone at 1 to 2 mg/kg/day or equivalent.
- If still no improvement within 2 to 3 days despite 1 to 2 mg/kg/day methylprednisolone IV or equivalent, promptly start treatment with an immunosuppressants (e.g., mycophenolate mofetil 0.5 – 1 g every 12 hours then taper in consultation with hepatology consult). Discuss with study physician if mycophenolate is not available. Infliximab should NOT be used.
- Perform Hepatology Consult, abdominal workup, and imaging as appropriate.

Hepatitis (elevated LFTs)	Any Elevations of AST, ALT, or TB as Described Below	General Guidance	For Any Elevations Described

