
THIS shaded area is guidance only for management of “Hepatitis (elevated LFTs)” in HCC patients
 
Infliximab should not be used for management of immune-related hepatitis.
 
See instructions at bottom of shaded area
 
if transaminase rise is not isolated but (at any time) occurs in setting of either increasing bilirubin or signs of DILI/liver decompensation
		
General Guidance
 
For Any Elevations Described
 
 Monitor and evaluate liver function test: AST, ALT, ALP, and TB. Evaluate for alternative etiologies (e.g., viral hepatitis, disease progression, concomitant medications, worsening of liver cirrhosis [e.g., portal vein thrombosis]). For HBV+ patients: evaluate quantitative HBV viral load, quantitative HBsAg, or HBeAg. For HCV+ patients: evaluate quantitative HCV viral load. Consider consulting Hepatology or Infectious Diseases specialists regarding changing or starting antiviral HBV medications if HBV viral load is >2000 IU/ml. Consider consulting Hepatology or Infectious Diseases specialists regarding changing or starting antiviral HCV medications if HCV viral load has increased by ≥2-fold. For HCV+ with HBcAb+: Evaluate for both HBV and HCV as above. 	

Isolated AST or ALT >ULN and $\leq 5.0 \times \text{ULN}$, whether normal or elevated at baseline
		
 No dose modifications. If ALT/AST elevations represents significant worsening based on investigator assessment, then treat as described for elevations in the row below. For all transaminase elevations, see instructions at bottom of shaded area if transaminase rise is not isolated but (at any time) occurs in setting of either increasing bilirubin 	

or signs of DILI/liver decompensation		

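### The Hy's law permanent-stop clause is printed only in the Grade 2 hepatitis cell; the Grade 3 hold-and-resume branch overlaps it with no exception, and section 10.3.3.2 is not linked to either

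*Protocol*

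**What the plan says.** Four places in the protocol bear on a combined rise in transaminases and bilirubin.

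- **Appendix 1, hepatitis (elevated LFTs), Grade 2 cell.** Study drug is held until recovery. If the toxicity worsens, the case moves to the Grade 3 or 4 instructions. The last bullet reads: "Permanently discontinue study drug/study regimen for any case meeting Hy's law criteria". The criteria are AST and/or ALT above 3 × ULN with bilirubin above 2 × ULN, no initial cholestasis, "and in the absence of any alternative cause".
- **Same table, Grade 3 cell.** For transaminases up to 8 × ULN, or bilirubin up to 5 × ULN, drug is held. The cell then says "Resume study drug/study regimen if elevations downgrade to Grade" 1 or below "or baseline within 14 days and after completion of steroid taper". Without that recovery in 14 days, treatment ends. Above 8 × ULN for transaminases, or above 5 × ULN for bilirubin, drug is discontinued. Hy's law is not mentioned.
- **Section 10.1.3.** "Hepatic function abnormality is defined as any increase in ALT or AST to greater than" 3 × ULN with concurrent total bilirubin above 2 × ULN, within an 8-day window. There is no cholestasis condition. For management the section points to 10.3.3.2.
- **Section 10.3.3.2.** If no definitive diagnosis is established, "dosing of the study subject must be interrupted immediately" and investigations begin. If an unrelated diagnosis is established, continuing is left to the investigator. The section mentions neither permanent discontinuation nor Appendix 1.

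Section 4.3, item 5, sends the reader to section 10.3 for the adverse-event criteria that end treatment. Appendix 1 also has a second hepatitis panel that repeats the Hy's law clause, but it opens "THIS shaded area is guidance only for management of" hepatitis in patients with hepatocellular carcinoma, who are not this trial's population.

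**The concern.** Whether treatment ends for good after a serious liver signal should not depend on which page a site opens. As printed, a site that follows the Grade 3 row, or that goes from section 10.1.3 to 10.3.3.2, could restart a patient whom the clause in the Grade 2 cell stops. Read row by row, the table can also treat a worse case more leniently than a milder one.

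The setting is relevant. Hepatitis and transaminase increases are listed adverse events of special interest in section 10.1.3. Section 4.1 admits patients with liver metastases at AST/ALT up to 5 × ULN, so some may already exceed the 3 × ULN limb at entry. They should not enter with both limbs met, because the same section caps bilirubin at 1.5 × ULN outside confirmed Gilbert's syndrome. About 20 sites will apply these rules.

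**Working it through.** No sample-size or error-rate figure is involved. The check compares the printed thresholds and follows the cross-references. Write T for transaminases and B for bilirubin, both in multiples of ULN.

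**1. Rules as printed**

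| Place | Trigger | Action |
|---|---|---|
| Appendix 1, Grade 2 cell, Hy's law bullet | T > 3 and B > 2, no initial cholestasis, no alternative cause | Permanent stop |
| Appendix 1, Grade 3 cell, first branch | T ≤ 8 or B ≤ 5 | Hold; resume on recovery within 14 days and after steroid taper |
| Appendix 1, Grade 3 cell, second branch | T > 8 or B > 5 | Discontinue |
| Sections 10.1.3 and 10.3.3.2 | T > 3 and B > 2, no definitive diagnosis | Interrupt and investigate; no end point stated |

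**2. Overlap of the Hy's law bullet with the Grade 3 resume branch**

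Both apply to a case graded 3 with 3 < T ≤ 8 and 2 < B ≤ 5, without cholestasis or another cause. Take T = 7 and B = 4:

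- Hy's law: 7 > 3 and 4 > 2, so the criteria are met.
- Grade 3 first branch: 7 ≤ 8 and 4 ≤ 5, so hold-and-resume applies.
- Grade 3 second branch: 7 is not above 8 and 4 is not above 5, so it does not apply.

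A milder case at T = 4 and B = 2.5, if graded 2, meets the Hy's law bullet in its own cell and is stopped. The grades in both examples are assumptions: the protocol refers to CTCAE v4.03 and does not print the cut-offs.

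**3. The *or* in the Grade 3 cell**

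The first branch needs only one limb at or below its limit. The second needs only one limb above. Any case with one limb on each side satisfies both. Take T = 10 and B = 4:

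- First branch: 4 ≤ 5, so hold and possibly resume.
- Second branch: 10 > 8, so discontinue.

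Only cases with T ≤ 8 and B ≤ 5, or with T > 8 and B > 5, fall in a single branch.

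**4. Cross-references**

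- 10.1.3 leads to 10.3.3.2, and 10.3.3.2 does not lead on to Appendix 1.
- 4.3 item 5 leads to 10.3, and 10.3.3.2 holds no permanent-stop criterion for this event.
- 10.1.3 has no cholestasis condition and the Hy's law bullet has one, so the two populations differ although the thresholds match.

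**5. Cut-offs**

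Section 10.1.3 uses strictly greater than 3 × and 2 × ULN. The SAE sentence in 10.3.3.2 uses 3 × and 2 × ULN or more. They differ only when a value is exactly 3 × or 2 × ULN.

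**The case against.** The clause says any case, and those words are not limited to Grade 2. Read as a specific rule qualifying a general one, it can govern Grade 3 as well, and the Grade 3 cell nowhere says that a Hy's law case may resume. This stands in part: a reader might infer that the protocol expressly permits restarting such a patient, and it does not. What remains is a clause in one cell, an instruction that moves worsening patients out of that cell, and a destination cell that is silent.

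Interruption in 10.3.3.2 can precede a permanent stop, since excluding other causes takes work-up, and sections 6.2.1 and 10.1.3 elsewhere send dose modification and immune-related events to Appendix 1. This also stands in part. The fault in 10.3.3.2 is a missing link and end point rather than an opposite instruction. But the sentence in 10.1.3 on this particular event points to 10.3.3.2 alone.

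A reader might also infer that 10.3.3.2 contradicts itself on reporting, because it requires a 24-hour report and then says such cases "may need to be reported as SAEs". It does not. The first duty is to notify the laboratory event as a hepatic function abnormality; the second sentence concerns classification as an SAE. Both can stand, and the section already states by grade, hospitalisation and medical importance when an event is an SAE.

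The table was read from a PDF, so cell boundaries could be questioned. The bullet's position among the Grade 2 instructions, before the Grade 3 label, makes the placement clear enough.

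**Conclusion.** The point holds as an unresolved overlap within the Appendix 1 hepatitis table and a broken chain between sections 4.3, 10.1.3, 10.3.3.2 and that table. It covers cases graded 3 with transaminases above 3 and up to 8 × ULN and bilirubin above 2 and up to 5 × ULN, without cholestasis or another cause, plus Grade 3 cases with one limb on each side of the 8 × and 5 × limits. The extent in practice rests on the assumed CTCAE grades.

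The documents give no frequency for the combined elevation. It is tempting to derive one from the serious liver reactions listed for the combination in section 1.4.2.3, but those are counts by preferred term and do not show which patients had both limbs raised. No expected number for this trial can be drawn from them, nor do they support a statement about how such a case would end.

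The documents do not settle which action is intended, and this review does not say. The cut-off mismatch is secondary.

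**What to change.** Reconcile section 4.3 item 5, section 10.1.3, section 10.3.3.2 and the Grade 2 and Grade 3 cells of the non-HCC hepatitis table. The sponsor decides which action holds. The reconciled text should state:

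- whether the Hy's law clause applies to cases in the Grade 3 row;
- how the *or* in the two Grade 3 branches is to be read when one limb is above its limit and the other is not;
- whether the cholestasis condition applies to the event defined in 10.1.3;
- what follows the interruption in 10.3.3.2, with a cross-reference to Appendix 1, so that the pointer in 4.3 leads to a criterion.

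As a secondary change, use the same inequality in 10.1.3 and 10.3.3.2. The SAE sentence and the 24-hour notification can otherwise stay.

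The cost is wording. AST, ALT and total bilirubin are already in the chemistry panel (Table 5). Because the text bears on subject safety, it would follow the amendment route in section 12.4. Appendix 1 describes itself as an annex shared across trials of these drugs; if its text cannot be altered, a clarifying note in the protocol body would serve.
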